8.3 Study procedures

Patient's timeline

Patient timeline

The study flow and timeline are depicted above. After inclusion in the study, both the control and the study (intervention) group will fill in a questionnaire. This start-questionnaire will consist of questions regarding self-efficacy (ESES questionnaire) and demographics. Subsequently, they will either follow regular treatment (control) or receive our product and follow rehabilitation aided by the sticky reminders + app. After 4 weeks, the test period is over and patients will take part in evaluation. The evaluation for the control group consists of only one component: a questionnaire. This end-questionnaire is identical to the start-questionnaire and consists of questions regarding self-efficacy (ESES). For the intervention group, the evaluation consists of two components: a questionnaire and a semi-structured interview. This end-questionnaire consists of questions regarding self-efficacy (ESES) and system usability (SUS). The above described is summarized in the table below. The measurements and assessments are described in more detail under the headings “Parameter assessments” and “Measurements” below.

Physiotherapists’ assessment

The physiotherapists will fill in a questionnaire (SUS) and will be interviewed in a semi-structured way. The above described is summarized in the table below. The measurements and assessments are described in more detail under the headings “Parameter assessments” and “Measurements” below.

| Group | Start evaluation | End evaluation |
|-----------------|--|---|
| Control | Questionnaire: ESES + Demography | Questionnaire: ESES |
| Intervention | Questionnaire: ESES + Demography | Questionnaire: ESES + SUS Semi-structured interview |
| Physiotherapist | N/A | Questionnaire: SUS Semi-structured interview |

Parameter assessments

- Self-efficacy will be determined with the validated Dutch translation of the Exercise Self-Efficacy Scale and analysed with a social-cognitive model of health behaviour change theory. In this theory, self-efficacy is seen as a predictor, mediator or moderator (Burke *et al.*, 2008; Schwarzer, 2008) on health behaviour.
- Usability will be determined using the System Usability Scale, developed by J. Brooke, and by interviewing patients and physiotherapist in a semi-structured way based on a healthcare adapted UTAUT2 framework (Slade *et al.*, 2013).
- Scanning the stickers is registered in the application. Using the registrations gathered by the app, the extent to which and how the app is used can be derived and correlated to possible effects on self-efficacy. This way, we can determine whether and how much the app is used, and thus whether we can link observed group effects to intervention use.
- Using the aforementioned gathered data and subsequent analyses, we will assess the feasibility.
- Demography data will be gathered by questions regarding this topic.

Measurements

Exercise Self Efficacy Scale (ESES)

Self-efficacy will be determined with the Dutch translation of the Exercise Self-Efficacy Scale, developed and validated in spinal cord injury by Nooijen *et al.* The ESES consists of 10 items about level of self-confidence with regard to performing regular physical activities and exercise (17). A sample item is: "I am confident that I can overcome barriers and challenges with regard to physical activity and exercise if I try hard enough". Respondents answer using a 4-point scale: not at all true, rarely true, sometimes true, and always true. The minimum score is 10 and the maximum score 40. A higher score indicates higher exercise self-efficacy (Nooijen *et al.*, 2013).

System Usability Scale (SUS)

[figure not shown]
We will assess usability with a Dutch translation of the validated System Usability Scale (SUS) questionnaire. The SUS gives a global view of subjective assessments of usability (Brooke, 1996). This simple questionnaire consists of 10 items with five response options; from 'strongly agree' to 'strongly disagree'. The scores range from 0 to 100, with a score of 68 considered average.

Demographics

A few generic demographic parameters will be asked in the start questionnaire for both the intervention and control group. These include age, gender, medical history (regarding physiotherapy) and highest educational level.

Semi-structured interviews

We will evaluate patients' and physiotherapists' experiences with the sticky reminders + app by means of semi-structured interviews. The interview guides (for patient or physiotherapist) are developed following the UTAUT2 framework, which indicates acceptance of a technological innovation in healthcare and is depicted below (Slade et al., 2013). The interview guide is attached as a separate document in Dutch. We will focus on the topics performance expectancy, effort expectancy, social influence, facilitating conditions, hedonic motivation and habits. During the conversations, we might touch upon price value, but this is not our initial interest. Patients will be interviewed once the intervention phase has ended. Interviews will take approximately 30-60 minutes. In particular, we will focus on advantages and disadvantages of using the sticky reminders in daily practice, and users' expectations for the future. All interviews will be performed face-to-face, recorded and transcribed verbatim. Subsequently, two investigators will systematically analyse all interviews using analysis software (e.g. ATLAS.ti).

Frequency of use

We will use logging data from the app to assess frequency of use.

8.4 Withdrawal of individual subjects

Subjects can leave the study at any time for any reason if they wish to do so without any consequences. They will receive the possibility to have their data deleted, which will then not be used in the study. The investigator can decide to withdraw a subject from the study for urgent medical reasons.

8.4.1 Specific criteria for withdrawal (if applicable)

Not applicable

8.5 Replacement of individual subjects after withdrawal

Given that this is a feasibility trial, dropouts will not be replaced.

8.6 Follow-up of subjects withdrawn from treatment

Subjects withdrawn from the trial or discontinuing, will be asked to complete the after trial measurements. However, if they have addressed the desire to have their data deleted, these after trial measurements will not be asked for.

8.7 Premature termination of the study

Despite being an unexpected scenario, the study will be terminated when an increased amount of injuries linked to the intervention occurs in the intervention group. Physiotherapists will report this scenario to the research group when applicable.

9. SAFETY REPORTING

9.1 Temporary halt for reasons of subject safety

In accordance to section 10, subsection 4, of the WMO, the sponsor will suspend the study if there is sufficient ground that continuation of the study will jeopardise subject health or safety. The sponsor will notify the accredited METC without undue delay of a temporary halt including the reason for such an action. The study will be suspended pending a further positive decision by the accredited METC. The investigator will take care that all subjects are kept informed.

9.2 AEs, SAEs and SUSARs

9.2.1 Adverse events (AEs)

Adverse events are defined as any undesirable experience occurring to a subject during the study, whether or not considered related to the use of sticky reminders and/or the prototype user app. All adverse events reported spontaneously by the subject or observed by the investigator or his staff will be recorded.

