3. STUDY DESIGN

This pilot is a controlled mixed methods feasibility trial.

The Radboudumc department REshape & Innovation Center in collaboration with two physiotherapy departments will execute the pilot. The envisioned duration of the project is five months. Patients will be included in April and May 2018, after which we will analyse data and publish results. The product-testing period is 4 weeks per patient. There will be an intervention group and a control group. The control group will only execute point 1 and 5 in the research design described below besides their regular treatment (excluding interview and SUS component). The control group is present to exclude conclusions based on treatment effects instead of intervention effects. The intervention group will go through all five steps. Millen et al. chose a similar study design, where they measured self-efficacy in cardiac rehabilitation (Millen *et al.*, 2009).

In the present course of therapy, supporting their home exercise program, patients suffering from Neuralgic Amyotrophy or a lower extremity amputation (using a socket or an osseointegrated prosthesis) receive a folder with written instructions on performing the exercises which can be consulted when needed. Patients give feedback during every hospital visit regarding their exercises and progression. In these sessions, the physiotherapist asks for information on the whole week schedule, whereas for patients it is hard to remember the exercises of the beginning of the week. To improve this, the osseointegrated prostheses patients keep a daily paper-based diary for pain scale, pain location, prosthesis wearing time and time spent on muscle exercises and standing or walking. Apart from this, patients do not register or monitor their progress in current course of therapy.

The introduction of the sticky reminders in combination with the app alters the method of registration compared to the present course, but the overall process remains the same. *Instead of written or spoken instructions and feedback, this information will be digitally provided and available.*

The patient process is described and depicted below.

1. **Baseline measurement:** To monitor self-efficacy patients are asked to fill out a validated self-efficacy questionnaire. This outcome is supposed to be the baseline value of the pilot. For extra information regarding the patient, demographic questions will be included in the questionnaire.

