2. **Technology introduction:** In the first hospital visit, the patient will get all the necessary or desired information on the new technology. Following this meeting, patients have time to decide whether they want to participate in the pilot. After inclusion, patients receive help for installing the app and will get an introduction on how to use the application.
3. **Home registration:** After the regular physiotherapy appointment in the hospital, patients will receive exercises to execute in the home situation. These exercises are also linked to at least one NFC tag. These NFC tags are illustrated with a location, suitable for the exercises. Patients will discuss their personal appropriate locations for the NFC tags with their physiotherapist. When walking by the NFC tag, the patient can scan the tag with their personal smartphone, showing them a video of the corresponding exercise. All information that was previously provided in the folder is now handed to the patient via the video. The application registers the scanning of the tag on a secure server. If no prescribed exercises are performed within a predefined timeslot, the app will send a one-time push notification to the patient. At the end of the day, a tag will be scanned to show the daily report form. This daily report contains questions matching the regular treatment supplemented with questions on efficacy.
4. **Physiotherapy session:** Back in the hospital setting, the regular treatment is continued and the progress of the rehabilitation will be discussed. The app can support this session by presenting graphic representations of the daily feedback gathered with the daily reports. Step 3 and 4 will be repeated until the NFC tag trial period is over.
5. **Evaluation:** In the end, the questionnaire answered at the start is repeated as an end-measure, supplemented with a system usability scale (SUS) questionnaire. Elaborate opinions will be gathered by interviewing patients and physiotherapists in a semi-structured way. In semi-structured interviewing, a guide is used, with questions and topics that must be covered.

Sticking to your Exercises

[figure not shown]
However, in contrast to structured interviews, this conversational style of interviewing allows for gathering elaborate opinions.

The timeline is shown below. The control group and intervention group will undergo a different timeline:

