Patient: Sees how many exercises are provided to him/her and how much he/she still needs to accomplish on a daily basis. The patient can also provide feedback to the physiotherapist and to themselves via daily reports or log-ins. In addition, the app will show a timeline with desirable targets, which should provide an extra motivation to perform the exercises.

Physiotherapist: Physiotherapists can easily connect the appropriate video and sticker combination at the desired moment in the rehabilitation via a web-interface. The physiotherapist can log in to this interface and see all the appropriate anonymized patients (per disorder). For each patient, the physiotherapist can look into collected data on log-ins and daily reports, and adapt the therapy accordingly if necessary.

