13. STRUCTURED RISK ANALYSIS

13.1 Potential issues of concern

a. Level of knowledge about mechanism of action

Not applicable, not an invasive or biological product.

b. Previous exposure of human beings with the test product(s) and/or products with a similar biological mechanism

Not applicable, not an invasive or biological product.

c. Can the primary or secondary mechanism be induced in animals and/or in *ex-vivo* human cell material?

Not applicable, not an invasive or biological product.

d. Selectivity of the mechanism to target tissue in animals and/or human beings

Not applicable, not an invasive or biological product.

e. Analysis of potential effect

Not applicable, not an invasive or biological product.

f. Pharmacokinetic considerations

Not applicable, not an invasive or biological product.

g. Study population

Our population will consist of rehabilitating patients in stable conditions apart from the disorder they receive physical therapy for (either neuralgic amyotrophy or leg amputation and prosthesis). We do not expect any negative (medical) events during the test period since the intervention is non-biological and non-invasive. A (minimal) risk that is present for patients is wrong positioning of the stickers. Further, risks can include privacy issues and unexpected events can always occur (e.g. falling off of stairs when scanning a sticker is located to the stairs). Should such events occur and be attributable to the research in any way, these events will be handled appropriately.

h. Interaction with other products

No interaction with other products is expected, as this product is a non-invasive, non-biological product.

i. Predictability of effect

Not applicable, not an invasive or biological product.

j. Can effects be managed?

Not applicable, not an invasive or biological product.

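### Injuries are recorded only if someone volunteers or notices them and no questionnaire asks about them, so the injury record may be incomplete and is not comparable between arms; separately, the termination statement in 8.7 gives no reference for an increase

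*Protocol*

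**What the plan says.** **Capture.** Section 9.2.1 defines adverse events broadly, whether or not they are thought related to the stickers or app. The method is unsolicited: "All adverse events reported spontaneously by the subject or observed by the investigator or his staff will be recorded".

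**Scheduled instruments.** The table in section 8.3 lists ESES and demography at the start and ESES at the end, with SUS and an interview added for the intervention group. Of the controls it says: "The evaluation for the control group consists of only one component: a questionnaire". No instrument contains a fall or injury item.

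**Intervention-only contact.** Section 3, step 3: "At the end of the day, a tag will be scanned to show the daily report form". Section 6.1 adds: "For each patient, the physiotherapist can look into collected data on log-ins and daily reports, and adapt the therapy accordingly if necessary". The data table in section 12.1 lists a pain score for both patient groups, and pain location and medication for amputees. It lists no fall or injury field. An interview of 30 to 60 minutes follows the intervention phase (8.3).

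**Named risks.** Section 6.4 describes injury from exercising at a mismatched location. Section 13.1 gives the example "falling off of stairs when scanning a sticker is located to the stairs".

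**Termination.** Section 8.7: "the study will be terminated when an increased amount of injuries linked to the intervention occurs in the intervention group". It continues: "Physiotherapists will report this scenario to the research group when applicable".

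**The concern.** The protocol foresees specific physical hazards and makes continuation of the study depend on injuries, but plans no occasion on which a patient is asked about one. Minor falls at home may never reach the record in either arm.

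The arms also differ in how often something might prompt a report. A pain entry in the app can lead the physiotherapist to ask what happened, and the interview looks for negative effects. A control has neither prompt. With open allocation, staff may also be more alert to injuries in one arm than in the other.

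Two things are at stake. A real problem could go unrecorded, and a crude count by arm, if anyone drew one up, could not be read as a difference in risk. No later analysis can recover events that were never elicited, so this cannot be left to an analysis plan. There is no safety committee (9.5) and monitoring is marked as not applicable (12.2), so little else would fill the gap.

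**Working it through.** The protocol gives no injury rate, threshold or safety power, so there is no figure to reproduce. The check compares the sections and then illustrates the size under stated assumptions.

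**1. Contact over the 4 weeks (28 days)**

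| Source | Control | Intervention |
|---|---|---|
| Regular sessions, prosthesis wearers (6.1: twice a week) | 4 × 2 = 8 | 8 |
| Regular sessions, NA (6.1: biweekly, read as every two weeks) | 28 / 14 = 2 | 2 |
| Daily app report (3, step 3) | 0 | 28 × 1 = 28 |
| End interview (8.3) | 0 | 1 |
| Scheduled fall or injury question | 0 | 0 |

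In-person contact is equal apart from the interview. The difference lies in study-specific contact. One qualification applies: osseointegrated-prosthesis patients already keep a daily paper pain diary in usual care. Section 3 adds that patients otherwise do not register their progress, so NA and socket-prosthesis controls have no equivalent.

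**2. What unequal capture would do**

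Let both arms have true injury risk p, with recording probabilities c_C (control) and c_I (intervention). The apparent risk ratio is (p × c_I) / (p × c_C) = c_I / c_C, whatever p is. The capture values are assumptions.

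- 80% v 90%: 0.9 / 0.8 = 1.125, about 1.1
- 50% v 70%: 0.7 / 0.5 = 1.4
- 50% v 100%: 1.0 / 0.5 = 2.0

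**3. How often the intervention arm would show more recorded injuries by count**

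Section 4.4 gives 30 patients in total without a split; 15 per arm is assumed. With X_C ~ Bin(15, p × c_C) and X_I ~ Bin(15, p × c_I), independent, P(X_I > X_C) is:

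| Capture C v I | p = 0.1 | p = 0.2 | p = 0.3 |
|---|---|---|---|
| 50% v 50% | 0.32 | 0.38 | 0.40 |
| 90% v 90% | 0.37 | 0.41 | 0.42 |
| 80% v 90% | 0.40 | 0.46 | 0.49 |
| 50% v 70% | 0.42 | 0.52 | 0.58 |
| 50% v 100% | 0.56 | 0.70 | 0.78 |

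A small gap barely moves the result away from equal capture. A large gap moves it a lot.

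**4. Direction**

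The documents do not fix this either. Section 3 says digital information takes the place of written or spoken instructions and feedback, and the listed app fields include no injury item. Capture could therefore be lower in the intervention arm, in which case the ratios invert: 0.8 / 0.9 = 0.89 and 0.5 / 1.0 = 0.5.

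**5. The termination wording**

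Section 8.7 counts injuries linked to the intervention, in the intervention group. A control patient has no stickers and cannot have such an injury, so the control arm gives no baseline for that count. No historical rate, number, time window or method of attribution is stated. This gap exists however well injuries are captured.

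**The case against.** A reader might infer that unequal contact is what makes the termination rule unusable. The text does not support that. Section 8.7 names no comparison with the control arm. It counts attributed injuries in one group, so control-arm capture does not enter the rule as written. Incomplete capture and the missing reference are two separate defects, and that objection stands.

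A reader might also infer that intervention patients are simply seen much more. They are not. The physiotherapists who would raise the alarm see both arms on the same regular schedule (3, 6.1), and the only added visit is the interview, after that patient's 4 weeks. It also stands that nothing in the app form asks about falls, and that physiotherapists in usual care ask about the past week's exercises at each visit. That is a real prompt in both arms, though not a question about injury.

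It can further be said that no between-arm safety analysis or claim of no harm is planned, and that for a 30-patient pilot of stickers and an app, solicited events are a matter of preference. The first part is correct, and it limits the consequence. The second goes too far. The protocol names these hazards itself and lets the study's continuation rest on them, and asking takes almost no effort.

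On timing, the interview cannot help the patient being interviewed, but enrolment over April and May (3) means early interviews could still inform a decision while later patients are in the study.

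**Conclusion.** The point holds in a limited form. Capture of injuries is passive and no instrument asks about them, although the protocol names them as risks. Because app reports and interviews exist only in an unblinded intervention arm, recorded injuries may be incomplete and should not be compared between arms as though equally ascertained.

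Neither the size nor the direction of any bias follows from the documents. The apparent ratio of about 1.1 to 2.0 rests wholly on assumed capture rates and on the assumption that capture is better in the intervention arm. The probabilities of a higher count also assume 15 per arm and equal true risk of 10% to 30%. They show what is possible and do not predict what this study would find.

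Independently, the increase in 8.7 has no stated reference. The documents do not support the stronger conclusion that differential contact biases the termination decision.

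This is worth correcting because it cannot be repaired after data collection. It does not affect the self-efficacy endpoint.

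**What to change.** 1. Put the same short question to both arms, at regular physiotherapy visits and in the end questionnaire: any fall or injury during home exercise, how many, and where. The visit question is the one that can inform a decision while a patient is still in the study; the end item catches what was missed.
2. Tabulate all injuries by arm regardless of attribution, and record any judged link to the stickers or app as a separate variable. This fits the broad definition already in 9.2.1.
3. Have the sponsor reconcile the wording of 8.7 with that record and state what an increase refers to. No threshold or stopping rule is proposed here.

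**Cost:** one question, one table and a clarified sentence; under a minute per patient. More minor events may be recorded. The fix makes capture equal by design. It does not make a study of this size able to rule out a difference in injury risk.
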